# **Exploratory Analyses:**

To study the efficacy of CBD on the aspects of PD listed in Section IV, 1.4 and plasma levels of cytokine in PD.

**Exploratory Outcome Measures:** The efficacy of CBD on these aspects of PD are measured by the same standardized tools used for safety and tolerability (listed in Section IV, 1.4). The effect of CBD is also measured by Clinical Global Impression (CGI) and Patient Global Impression-improvement (PGI-I) and Change (PGI-C). CGI is a three-item observer-rated scale that measures illness severity (CGIS), global improvement or change (CGIC) and therapeutic response. The CGI is rated on a seven-point scale, with the severity of illness scale using a range of responses from 1 (normal) through to 7 (amongst the more severely ill patients). CGI-C scores range from 1 (very much improved) through to 7 (very much worse). Treatment response ratings should take account of both therapeutic efficacy and treatment-related adverse events and range from 0 (marked improvement and no side-effects) and 4 (unchanged or worse and side-effects outweigh the therapeutic effects). Each component of the CGI is rated separately. PGI-I is a global index that may be used to rate the response of a condition to a therapy (transition scale). It is a simple, direct, easy to use scale that is intuitively understandable to patients. PGI-C is rated on a seven-point scale, evaluating all aspects of patient' health and determining if there has been an improvement or not. The change from baseline to the end of 2.5 mg/kg/day is compared between the two groups.

Change of plasma levels of cytokine from baseline to the end of 2.5 mg/kg/day will be compared between the two groups.

Assessments	Primary	Secondary	Exploratory
	(efficacy)	(safety +tolerability)	(efficacy)
MDS UPDRS Part III motor score	Х		
MoCA		X	Х
Detailed cognitive battery		X	Х
Anxiety short form		X	Х
NPI		X	Х
SCOPA-Sleep		X	Х
Sleep sub-study		X	Х
Stanford Sleepiness Scale (SSS)		X	
"Alertness Test"			
Depression short form		X	Х
Emotional and Behavioral		X	Х
dyscontrol short form			
Fatigue Severity Scale		X	Х
Pain Intensity 3a and Interference		X	Х
4a short forms			

 Table 5. Measurement tools performed in current study.

	1
Х	Х
X	Х
X	Х
X	Х
Х	Х
Х	Х
X	Х
X	
X	Х
X	Х
X	Х
	Х
	Х
	Х
X	Х
	Х
	X X X X X X X X X X

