Visit 2- Baseline visit: Eligibility confirmation (including tremor evaluation), medical history, concomitant medications collection, formal drug interaction assessment, vital signs, orthostatic blood pressures, brief physical exam, MoCA, MDS-UPDRS, H&Y rating, UDysRS, NMSS, OABSS, tremor constancy and amplitude two hours after taking study drug, TUG test, cognitive assessment battery (including tests of verbal intellectual function, attention, processing speed, executive function, verbal learning and memory, visuospatial memory, speeded verbal fluency, and word retrieval), Anxiety short form, Depression short form, SCOPA-Sleep, ISI, DBAS-16, Pittsburgh Sleep Quality Index, Alertness test, RBDSQ, C-SSRS, IRLS, Fatigue severity scale, Pain intensity and interference short form, PDQ-39, EQ-5D, CGI, PGI, urine drug (THC) test (urine dipstick test), urine pregnancy test (women childbearing potential) and study drug dispensing is done and, if appropriate, randomization. Skin evaluation (Dermatology Intake Form, DLQI, and dermatology

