- 2. Vital signs, orthostatic blood pressures, physical exam, EKG, and labs (hematology, complete metabolic profile, urinalysis) will be done during study visits. For vital signs and labs, data will be analyzed as a simple two-period trial. Means and confidence intervals will be presented pre and post treatment by treatment group, and for the change scores by treatment group. A two independent sample T-test will compare the means of the change scores between the treatment groups. More complex situations can be analyzed with longitudinal regression models.
- 3. Standardized assessment tools (MoCA, Cognition assessment battery, Anxiety short form, NPI, SCOPA-Sleep, ISI, DBAS-16, Pittsburgh Sleep Quality Index, RBDSQ, QUIP-RS, C-SSRS, Depression short form, Emotional Behavioral dyscontrol short form, Fatigue severity scale, MDS UPDRS, UDysRS, Pain Intensity 3a short form and Pain Intensity 4a short form, IRLS, PDQ-39 and EQ-5D-5L) and lab tests, the data will be analyzed as a simple two-period trial. Means and confidence intervals will be presented pre and post treatment by treatment group and for the change scores by treatment. A two independent sample T-test will compare the means of the change scores between the treatment groups. More complex situations can be analyzed with longitudinal regression models.
- 4. Proportion of participants who drop out of the study due to study drug intolerance. Analysis (proportions of participants who drop out of the study due to study drug intolerance in the two treatment groups) will be mostly descriptive, and proportions and confidence intervals will be calculated. Proportion differences between groups can be compared with the standard test.

**Exploratory Outcome Measures:** The efficacy of CBD on cognition, psychosis, sleep, daytime sleepiness, mood, fatigue, pain, impulsivity, other motor and non-motor PD signs, restless legs syndrome, REM sleep behavior disorder, quality of life, and plasma levels of cytokine are evaluated using the aforementioned assessment tools. The change from baseline to end of 2.5 mg/kg/day is compared.

Exploratory analyses: To study the efficacy of CBD on cognition, anxiety, psychosis, sleep, daytime sleepiness, mood, fatigue, pain, impulsivity, other motor and non-motor PD signs, restless legs syndrome, REM sleep behavior disorder, plasma levels of cytokine, and seborrheic dermatitis.

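### The change-from-baseline comparison is applied to global impression scales that already rate change, and PGI-I is scheduled at the baseline visit

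*Combined protocol and SAP*

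**What the plan says.** The exploratory part of Section IV.A adds three global scales to the standardized tools: CGI, PGI-I and PGI-C. It describes them as follows.

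- PGI-I: "PGI-I is a global index that may be used to rate the response of a condition to a therapy (transition scale".
- PGI-C: "PGI-C is rated on a seven-point scale, evaluating all aspects of patient' health and determining if there has been an improvement or not".
- CGI has three separately rated items. The severity item is a status rating, with the "severity of illness scale using a range of responses from 1 (normal) through to 7". The change item is different: "CGI-C scores range from 1 (very much improved) through to 7 (very much worse". The third item rates therapeutic response.

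The same paragraph then gives a single comparison for everything in it: "The change from baseline to the end of 2.5 mg/kg/day is compared between the two groups". Section F (Data Analysis Plan) repeats the rule for exploratory outcomes, without naming CGI or PGI: "The change from baseline to end of 2.5 mg/kg/day is compared".

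On timing, the Visit 2 (baseline) text in Section IV.C.1 includes "PDQ-39, EQ-5D, CGI, PGI, urine drug (THC) test", without saying which PGI or which CGI item. The Appendix 6 baseline list has CGI and PGI-I but no PGI-C. Its lists for the 1.25 and 2.5 mg/kg/day visits have CGI, PGI-I and PGI-C.

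**The concern.** A transition scale asks the rater to compare the present with an earlier state, so the rating is already a change. Subtracting a baseline rating produces a change in a change.

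The difficulty is plainest for PGI-I. It rates response to a therapy, yet it is scheduled on the day treatment starts, when there is no course of therapy to judge. Under the rule as written, a participant who marks improvement at Visit 2 and the same improvement at Visit 4 contributes zero.

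For PGI-C the rule and the schedule do not meet, because Appendix 6 provides no baseline value to subtract.

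What is at stake is the meaning of these exploratory comparisons, and possibly their precision. An analyst could also choose between scoring methods later. Section F plans no multiplicity adjustment across outcomes, so the scoring is better fixed beforehand.

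**Working it through.** **Rule against schedule**

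| Item | What it rates | At baseline? | Change from baseline meaningful? |
|---|---|---|---|
| CGI severity | status | CGI listed, item not named | yes |
| CGI-C | change | not stated | no |
| CGI therapeutic response | response to treatment | not stated | no |
| PGI-I | response to therapy | yes (Appendix 6) | no |
| PGI-C | change | not in the Appendix 6 list; the Visit 2 text says only PGI | no, and no value to subtract on that schedule |

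The Appendix 1 tick marks for these rows are not readable in the available text, so the absence of a baseline PGI-C rests on Appendix 6 alone. Section IV.C.1 has the first dose taken in clinic at Visit 2, so a PGI-I completed there follows one dose at most.

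**What subtraction could cost PGI-I**

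The plan gives no SD, correlation or effect size for these scales, so this is an illustration only. It borrows two figures from the primary outcome.

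- Completers: 30 per arm (Section IV.C.1).
- Standardized effect: 5.75 / 6.72 = 0.856 (Sample Size Justification). A two-sided two-sample t-test at alpha 0.05 needs 29.7, so 30, per arm for 90% power. This reproduces the plan's total of 60.

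Assume that effect on the Visit 4 rating itself, with no difference between arms in mean baseline rating. Let k be the baseline SD divided by the Visit 4 SD, and ρ the correlation between the two ratings. Then:

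SD of the difference = Visit 4 SD × √(1 + k² − 2ρk)

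effect after subtraction = 0.856 / √(1 + k² − 2ρk)

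| k | ρ | SD multiplier | Effect | Power, 30 per arm |
|---|---|---|---|---|
| 0 (constant baseline) | any | 1.000 | 0.856 | 90% |
| 0.5 | 0 | √1.25 = 1.118 | 0.766 | 83% |
| 0.5 | 0.3 | √0.95 = 0.975 | 0.878 | 92% |
| 1 | 0 | √2 = 1.414 | 0.605 | 64% |
| 1 | 0.3 | √1.4 = 1.183 | 0.723 | 79% |
| 1 | 0.5 | √1 = 1.000 | 0.856 | 90% |

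Subtraction adds no noise when k² − 2ρk ≤ 0, that is, when k = 0 or ρ ≥ k/2. With a smaller assumed effect of 0.5, power is 48% on the direct rating and 27% at k = 1, ρ = 0.

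**The case against.** The strongest defence is that the sentence is generic. It closes a paragraph that begins with the whole set of standardized tools, for most of which change from baseline is the normal measure. For PGI-C and CGI-C the rating is the change since baseline, and leaving PGI-C off the baseline list fits that intention. A reader might infer that the PGI-C outcome is simply undefined. The documents do not go that far: only a literal change score on the Appendix 6 schedule is impossible. The defence stands as a likely intent for PGI-C. It is not written down, and it does not explain why PGI-I is collected at baseline.

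A reader might also infer that CGI-C is rated at baseline and subtracted. The Visit 2 text and Appendix 6 say only CGI, and the components are rated separately, so the entry may mean severity alone. Nor does Appendix 6 show that PGI-I follows the first dose. Its list is not chronological: the urine THC test, an eligibility check, is also listed after dosing.

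Section F sends non-continuous exploratory outcomes to generalized estimating equations or generalized mixed models and allows non-parametric methods. Such models need not use subtracted scores. However, the section does not withdraw the change rule or exempt transition scales. A repeated-measures model that takes baseline PGI-I as its first time point and tests arm by time makes essentially the same comparison.

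Finally, baseline PGI-I ratings may cluster at no change, in which case subtraction costs nothing. That is correct, and it is why the loss of power can only be conditional.

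**Conclusion.** The point holds as a misfit between a stated rule and the scales it covers. It is firmest for PGI-I, which the plan itself classes as a transition scale, schedules at baseline and includes in a change-from-baseline comparison. For PGI-C, the rule cannot be applied literally on the Appendix 6 schedule, and the probable intent needs to be stated. For CGI-C and the response item, the rule is the wrong one, but whether a baseline rating exists is not stated.

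The change in meaning does not depend on any assumption. The loss of precision does. On the assumed effect of 0.856 it ranges from none to a fall in power from 90% to 64%, and some combinations show a slight gain. A reader might conclude that these outcomes are necessarily diluted; the documents give no SD or correlation to support that. The primary analysis and the sample size are untouched, so this is a minor clarification.

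**What to change.** In the exploratory part of Section IV.A, and in the matching text of Section F, state two things:

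1. PGI-I, PGI-C, CGI-C and the CGI therapeutic-response item are compared between arms on the rating given at the end of 2.5 mg/kg/day, by an ordinal or rank method (for example, a proportional-odds model or a Wilcoxon rank-sum test).
2. Change from baseline applies only to CGI severity.

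In the Visit 2 text and Appendix 6, state that of these global scales only CGI severity is collected at baseline. Alternatively, keep the baseline PGI-I and say that it is not used in the analysis. The second route suits a trial that has already started collecting data.

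The cost is a few sentences settled before unblinding and, on the first route, a small change to the Visit 2 schedule that removes a one-minute form. No useful information is lost.

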## **B.** Description of Population to be Enrolled:

Parkinson disease - Persons with PD have progressive disabling tremor, slowness, stiffness, balance impairment, cognitive deficits, psychiatric symptoms, autonomic dysfunction, fatigue, and insomnia. Tremor may interfere with necessary daily and work functions. The disorder affects approximately seven million people globally [Yao, S.C, et al. 2013; de Lau LM, et al. 2006]. PD usually begins around age 60, but it can start earlier. Treatment, typically medications such as levodopa and dopamine agonists, improve early stage symptoms. As the disease progresses and dopaminergic neurons continue to be lost, these drugs become less effective, and levodopa produces disabling motor fluctuations in most patients. PD invariably progresses with time. Untreated individuals are expected to lose independent ambulation after an average of eight years and be bedridden after ten years [Poewe W. 2006]. In people taking levodopa the progression of symptoms to a stage of high dependency from caregivers is on average 15 years.

#### C. Study Design and Research Methods C.1 Study design

The major purpose of this study is to assess the efficacy of CBD on motor symptoms of PD, and secondarily to study the safety and tolerability of CBD and other efficacy, particularly regarding tremor in PD. The study has been powered to detect a clinically significant reduction in MDS UPDRS Part III motor scores. This is a 1:1 parallel, double-blind, randomized controlled trial (RCT) with 60 participants. We will be recruiting up to 75 participants; the goal is to have 60 participants (30 in CBD group and 30 in placebo group) complete the study.

See Appendix 1 Schedule of Events for more detail on study design.

The study drug is obtained from NIDA. How the dose is started and escalated and what target dose is chosen is based on human literature and our open label study, as discussed in Section III under Discussion.

The study is a randomized, placebo controlled, double-blind parallel design with two treatment arms, each of approximately 2-3 weeks duration. In the 2-3 week treatment phase participants will start study drug and titrate up to the maximum tolerated or targeted dose (2.5 mg/kg/day of CBD). Each participant will have a screening visit, baseline visit within four weeks, 2 dose assessment visits (1.25 mg/kg/day and 2.5 mg/kg/day), and a safety visit (5 visits total). Participants will be evaluated at each dose level for monitoring adverse events, as well as changes in medical history and concomitant medications. Further, in case CBD alters the reliability of self - report, repeated measures will be taken on the third to fifth day at each dose during the clinic visits or at home. The assessments include the assessment of tolerability and symptoms of hepatotoxicity, SCOPA-sleep, Anxiety short form, Depression short form, Emotional and behavioral dyscontrol short form, and EQ-5D-5L. Participants are called 3 and 7 days after stopping the study drug to check for signs of withdrawal. At dose assessment visits, urinary CBD and metabolites will be tested. To maximize compliance the coordinator calls the participant to remind them the next day's clinical visit. To increase compliance with taking study drug, participants will be asked to fill out a diary at home. The diary will be a record of the date and time participants take study drug, dose of the study drug, and adverse and beneficial events. Study drug is dispensed at the baseline visit. Participants will measure their tremor using Tremor GUI MATLAB twice a day (two hours after breakfast dose and two hours after dinner dose) for two consecutive days after screening visit, three consecutive days prior to baseline and each dose assessment visit, as well as during the clinic visits. To evaluate the possible somnolence effect of CBD, participants will be evaluated their alertness before and three hours after they take the study drug at baseline visit.

# Inclusion and Exclusion criteria:

Inclusion criteria:

- Male or female participants 40 85 years of age.
- Willing and able to give informed consent (including through use of a legally authorized representative (LAR), if necessary).
- Idiopathic PD, per UK Parkinson's Disease Society (UKPDS) Brain Bank Clinical Diagnostic Criteria
- ON motor MDS UPDRS >20.
- Anti-parkinsonian medication is fixed for at least one month prior to the day the participant starts study drug treatment.
- If MoCA<22 participant must have a designated caregiver that agrees to ensure study protocols followed. This includes accompanying patient to study visits and being available for study phone calls.
- Must have a driver or available transportation (including provided Uber vouchers) to drive them to and from study visits and for other transportation needs during the treatment period.
- Has a significant other (someone who knows the participant well) that is appropriate for doing the NPI assessment, and agrees to do so
- Agrees to not take more than 1 gram per day of acetaminophen, due to a possible interaction with study drug that could increase risk of hepatotoxicity.

\*\*Note: the LAR (if required for informed consent), caregiver (required for those with MOCA<22), and significant other (required for all participants) may be the same person in some cases. In other cases, these may be different people.

Exclusion criteria:

- Known or suspected allergy to cannabinoids or excipients used in the study drug formulation.
- Cannabis is detectable at the screening visit by blood testing or at the baseline visit by urine testing. If cannabis is detected at either the screening or baseline visit, then the participant is a screen fail and may return >14 days later for a repeat screening visit. If cannabis is again detected at either the screening or baseline visit, then the participant is excluded and not allowed to rescreen.
- History of drug or alcohol dependence; defined by prior inpatient stay(s) for this or that patient states s/he has a history of this.
- Use of dopamine blockers within 180 days and cocaine, and MAO-A inhibitors within 90 days of baseline.
- Currently taking tolcapone, valproic acid, felbamate, niacin (nicotinic acid) at ≥2000 mg/day or nicotinamide (nicotinic acid amide or nicotinamide) at ≥3000 mg/day, isoniazid and ketoconazole due to risk of liver injury and clobazam and ketoconazole because of risk of toxic interactions with the study drug. These medications need to be stopped 90 days before the baseline visit.
- Unstable medical condition.
- Any of the following laboratory test results at screening:
  - $\Box$  Hemoglobin < 10 g/dL
  - $\Box$  WBC <3.0 x 10^9/L
  - $\Box$  Neutrophils <1.5 x 10^9/L
  - $\Box$  Lymphocytes < 0.5 x 10^9/L
  - $\Box$  Platelets <100 x 10^9/L
  - $\Box$  Hemoglobin A1C > 9%
- Aspartate aminotransferase (AST) and/or alanine aminotransferase (ALT) > 3 times the upper limit of normal. Persons with stable liver disease of known etiology can be included, unless total bilirubin or prothrombin time/INR is abnormal.
- Is pregnant or lactating, or has a positive pregnancy test result pre-dose.
- If a sexually active female, is not surgically sterile or at least two years post-menopausal, or does not agree to utilize an effective method of contraception from screening through at least four weeks after the completion of study treatment, using one of the following: barrier methods (diaphragm or partner using condoms plus use of spermicidal jelly or foam, preferably double-barrier methods); oral or implanted hormonal contraceptive; intrauterine device (IUD); or vasectomized male partner.
- Planned elective surgery during study participation.

Cytokines testing: Enrolled subjects who meet the following criteria will have blood collected for cytokines test, along with other blood tubes being collected, at screening and at 2.5 mg/kg/day dose assessment visit. If these criteria are not met at screening but are met at baseline visit, the draw for cytokines testing may be done at the baseline visit instead.

- Not currently taking or has not taken in the past 10 days chemotherapeutic or anti-inflammatory medications. A sample of such medications is listed in Appendix A, but it is not possible to list all medications in these broad classes. Thus, the PI will evaluate each subject's medications and decide if any meet this exclusion criteria.
- Does not have currently active cancer or is not currently being treated for cancer or inflammatory or atopic disease, listed in Appendix 8. It is not possible to list all such disorders, so the PI will evaluate each subject's medical status and decide if they have any meet that this exclusion criteria.
- No current kidney failure or renal dialysis, chronic respiratory disease requiring daily oxygen, active or treated seizures, and hyperthyroidism.
- No current or in the past seven days any infection, for example common cold or urinary tract infection, again to be at discretion of the PI.

Participants will be consented that the effects of CBD on driving are not known, that some users experience significant sedation but the effects vary among individuals and that participants should not drive while taking the study drug. A limited amount of Uber vouchers will be provided to subjects to assist with transportation needs during the treatment period. Alertness test will be done before and three hours after the first dosing is administered at baseline visit to judge the alertness degree for driving.

## Dose escalation strategy:

Study product (CBD or placebo) will be started at 1.25 mg/kg/day of CBD (once a day) for four days and then increase to 2.5 mg/kg/day of CBD (twice a day) for 10 (+4) days. Tolerability will be assessed at each dose during each clinic visit. Subjects may take a reduced dose for the duration of the study according to the investigator's medical judgement.

Regarding possible drug interactions, study pharmacists will be provided the calculated dose based on body weight, the list of the subject's medications, and additional relevant clinical information. The final study drug dose will be that recommended by the study pharmacists.

## Assessment of tolerability of each dose level

Tolerability will be assessed at each dose via collection of adverse events and administration of the standardized questionnaires by appropriate study staff during each clinic visit. Severity of adverse events will be graded according to the Common Terminology Criteria for Adverse Events (CTCAE), which is published by the National Cancer Institute (NCI) of the National Institutes of Health (NIH): Grade 1: Mild; asymptomatic or mild symptoms; clinical or diagnostic observations only; intervention not indicated.

Grade 2: Moderate; minimal, local, or noninvasive intervention indicated; limiting age-appropriate instrumental ADLs. Instrumental ADLs refer to preparing meals, shopping for groceries or clothes, using the telephone, managing money, etc.

Grade 3: Severe or medically significant but not immediately life-threatening; hospitalization or prolongation of hospitalization indicated; disabling; limiting self-care ADLs. Self-care ADLs refer to bathing, dressing and undressing, feeding self, using the toilet, taking medications, and not bedridden.

Grade 4: Life-threatening consequences; urgent intervention indicated.

Grade 5: Death related to AE.

The protocol for dose adjustments, maintenance, and discontinuation based on adverse effects is as follows:

- For participants with a grade 1 adverse event the dose will be increased by up to 1.25 mg/kg/day, or if they are on the maximal targeted dose (2.5 mg/kg/day) it will be continued.
- For participants with a grade 2 adverse event the dose will be reduced by 1.25 mg/kg/day or less.
- For participants with a grade 3 or 4 adverse event that the Investigator determines is unrelated, the dose will be continued. When the adverse event is stabilized or resolved, e.g., participant is stable after a hip fracture repair, the dose will be increased unless they are already on the maximum targeted dose.
- For participants with a grade 3 or 4 adverse event that the Investigator determines is related the study drug will be stopped and not restarted.

The Investigator will determine relatedness as described in Section IV. C.6, and will consider the adverse event related if she determines there is at least a reasonable possibility.

The major dose limiting effect, is somnolence. To monitor for this closely, the daytime sleepiness part to the SCOPA-sleep will be administered during each clinic visit, thus before each increase in dose. A score of >7 (note that the average score for PD is  $5.2 \pm 4$ ), if greater than before and considered problematic by the appropriate clinical staff, would result in the participant being instructed to drop to the prior dose for five more days before increasing the dose.

Liver function test is done at the study visit on the third to fifth day of each dose. Additional assessments of safety and tolerability is done at the study visit when the participant is on the maximum tolerated or targeted dose. The same protocol for dosing is applied for both adverse events found during study visits.

The CTCAE criteria are used to determine dose level adjustments and for participant and study stopping rules (Section IV C.5). Adverse events will be collected and reported as discussed in Section IV C.6.

Urine collection, storage and transfer for cannabis and metabolites test: The purpose of the urine cannabis and metabolites test is to develop a methodology to quantitate CBD metabolites. Participants will be given two urine cups, 100 mL each, at the baseline visit, 1.25 mg/kg/day dose assessment visit, and 2.5 mg/kg/day dose assessment visit. Urine cannabis and metabolites test will be done at dose assessment visits (1.25 and 2.5 mg/kg/day) and safety follow up visit. On the phone call before the day of dose assessment visits and safety follow up visit, participants will be reminded to collect urine in the morning of the study visit. They are asked to fill each up at least three-quarters full if possible, and to bring them to the visit (no refrigeration needed). Upon arrival of the visit the study coordinator will collect and store the urine cups in a -80°C freezer until shipment. For shipment, samples for each individual will be placed onto a sealable plastic bag together with an absorption pad. All the individual bags will be placed into a large sealable plastic bag with contains absorption material. Samples will be placed onto a Styrofoam box and will be shipped on dry ice. Urine samples will be labeled with the name of the study and the date and time of collection. Urine samples will be shipped for analysis to [name] at iC42 Clinical Research and Development. [name] is in charge of analyzing the specimens as well as contributing to interpreting results and writing publications. He receives only coded specimens with no PHI.

The blood and urine samples will be stored in [name] lab for possible unspecified future research under the consent of study subjects.

